2.1.7 Pharmacodynamics/genomics endpoints

Eotaxin-3, eosinophil cationic protein (ECP), total IgE and Thymus and Activation-Regulated Chemokine (TARC) will all be assayed at Visit 2(Week 0), Visit 8 (Week 12), Visit 11 (Week 24), Visit 14 (Week 36) and Visit 18(Week 52).

Periostin will be assayed at Visit 2(Week 0), Visit 4 (Week 4), Visit 8 (Week 12) and Visit 18(Week 52). And antigen-specific IgE panels will be collected at Visit 2(Week 0), Visit 8 (Week 12) and Visit 18(Week 52).

Blood eosinophil count will be measured as part of the standard 5-part WBC differential cell count on a hematology autoanalyzer.

Exhaled nitric oxide will be analyzed using a NIOX instrument (Aerocrine AB, Solna, Sweden), or similar analyzer using a flow rate of 50 mL/s, and reported in parts per billion (ppb). This assessment should be conducted prior to spirometry and following a fast of at least 1 hour at Visit 1(Week -4±1), Visit 2 (Week 0), Visit 3 (Week 2), Visit 4 (Week 4), Visit 8 (Week 12), Visit 9 (Week 16), Visit 10 (Week 20), Visit 11 (Week 24), Visit 14 (Week 36), Visit 17(Week 48), Visit 18(Week 52), Visit 19(Week 56), Visit 20(Week 60), Visit 21(Week 64)

Pharmacogenetic testing is optional and voluntary. A separate written informed consent form must be signed before sampling. For those patients who signed the optional pharmacogenetic informed consent form, blood samples for exploratory genetic analysis of DNA or RNA will be collected at the study visit as specified in the study flow chart, and these samples will be stored for future analysis.

2.1.8 Vaccine response

Subjects planning to receive vaccinations for tetanus (alone or combined), influenza, pneumococcus or meningococcus during the study may optionally sign a separate informed consent for collection of 2 blood samples for assay of vaccine IgG in serum for each vaccine: the first should be drawn within 6 weeks prior to vaccination and then the second should be drawn 3 to 4 weeks after vaccination (up to 6 weeks afterward allowed). Vaccinations should preferably occur after completion of at least 12 weeks of treatment, while remaining in compliance with the patient's recommended immunization schedule. Blood collections should be conducted at regularly scheduled study visits but, if this is not feasible, could also be done at unscheduled visits. The details on the date(s) of vaccination and the specific vaccines that are administered, such as brand and antigenic strains, should be collected (see [Appendix L](#)).

2.1.9 Health economic endpoints

A questionnaire of health care resource utilization (reliever medication, specialist visit, hospitalization, emergency or urgent medical care facility visit, outcome, sick leaves, school days loss, etc) will be administered at Visit 2 and every 4 weeks thereafter.

2.2 DISPOSITION OF PATIENTS

This section describes patient disposition for both patient study status and the patient analysis populations.

Screened patients are defined as any patients signed the informed consent.

Randomized patients consist of all patients with a signed informed consent form who have had a treatment kit number allocated and recorded in the IRT database, regardless of whether the treatment kit was used.

For patient study status, the total number of patients in each of the following categories will be presented in the clinical study report summary table:

- Screened patients
- Screen failure patients and reasons for screen failure
- Nonrandomized but treated patients
- Randomized patients
- Randomized but not treated patients
- Randomized and treated patients
- Patients who did not complete the 52-week treatment as per protocol
- Patients who discontinued study treatment by main reason for permanent treatment discontinuation
- Patients who withdraw from study prior to Week 52
- Patients who withdraw from study prior to Week 52 by main reason for study discontinuation.
- Patients who withdraw from study
- Patients who withdraw from study by main reason for study discontinuation
- Status at last study contact

For all categories of patients (except for the screened and nonrandomized categories) percentages will be calculated using the number of randomized patients as the denominator. Reasons for treatment discontinuation will be supplied in tables giving numbers and percentages by treatment group. This summary will be provided by treatment group and may also be further subgrouped by region/stratum as applicable.

All critical or major deviations potentially impacting efficacy analyses, randomization, and drug-dispensing irregularities, and other major or critical deviations will be summarized in tables giving numbers and percentages of deviations by treatment group.

Additionally, efficacy populations will be summarized by number of patients on the randomized population.

- Efficacy population: intent-to-treat (ITT) population

The analysis populations for safety, pharmacokinetics/pharmacodynamics will be summarized by number of patents on the safety population.

- Safety population
- PK population
- ADA population

2.2.1 Randomization and drug dispensing irregularities

Randomization and drug-dispensing irregularities occur whenever:

5. A randomization is not in accordance with the protocol-defined randomization method, such as a) an ineligible patient is randomized, b) a patient is randomized based on an incorrect stratum, c) a patient is randomized twice, or d) in a dynamic randomization scheme the treatment assignment is, in fact, not random, due to a computer program error.

OR

6. A patient is dispensed an IMP kit not allocated by the protocol-defined randomization, such as a) a patient at any time in the study is dispensed a different treatment kit than as randomized (which may or may not contain the correct-as-randomized IMP), or b) a nonrandomized patient is treated with IMP reserved for randomized patients.

Randomization and drug-dispensing irregularities will be monitored throughout the study and reviewed on an ongoing basis.

All randomization and drug-dispensing irregularities will be documented in the clinical study report. If the number of irregularities is large enough to make a tabular summary useful, the irregularities will be categorized and summarized among randomized patients (number and percentages). Nonrandomized, treated patients will be described separately.

Randomization and drug-dispensing irregularities to be prospectively identified include but are not limited to:

Randomization and drug allocation irregularities
Kit dispensation without IRT transaction
Erroneous kit dispensation
Kit not available

Randomization by error
Patient randomized twice
Stratification error
Patient switched to another site

2.3 ANALYSIS POPULATIONS

Patients treated without being randomized will not be considered randomized and will not be included in any efficacy population, but will be included in the safety population.

The randomized population includes any patient who has been allocated to a randomized treatment regardless of whether the treatment kit was used.

For any patient randomized more than once, only the data associated with the first randomization will be used in any analysis population. The safety experience associated with any later randomization will be assessed separately.

2.3.1 Efficacy populations

The primary efficacy analysis population will be the ITT population as defined in [Section 2.3.1.1](#).

2.3.1.1 Intent-to-treat population

The intent-to-treat population is the randomized population analyzed according to the treatment group allocated by randomization.

Patients will be analyzed in the treatment group to which they are randomized.

2.3.2 Safety population

The safety population is defined as:

- All patients who actually received at least 1 dose or part of a dose of the IMP, analyzed according to the treatment patients actually received.

In addition:

- Randomized patients for whom it is unclear whether they took the IMP will be included in the safety population as randomized
- For patients on placebo but accidentally exposed to dupilumab, the treatment group allocation for as-treated analysis will be the lowest exposed dupilumab dose group.
- For patients on placebo but accidentally exposed to the other placebo dose, the treatment group allocation for as-treated analysis will be the treatment as randomized.

- For patients on dupilumab but accidentally receive different treatment from the planned, the actual treatment group allocation for as-treated analysis will be the lowest exposed dupilumab dose group.

2.3.3 Population for pharmacokinetics/pharmacodynamics analyses

The **PK population** will consist of all patients in the safety population with at least one evaluable serum concentration data. Patients will be analyzed according to the treatment actually received.

ADA population will consist of all patients in the safety population who had at least one reportable ADA results (either ‘ADA negative’ or ‘ADA positive’) after first dose of the study treatment.

Biomarkers will be analyzed in the **exposed population**, consisting of patients in the safety population.

2.4 STATISTICAL METHODS

2.4.1 Demographics and baseline characteristics

Continuous data will be summarized using the number of available data, mean, standard deviation (SD), median, minimum and maximum for each treatment group. Categorical and ordinal data will be summarized using the number and percentage of patients in each treatment group.

Parameters will be summarized on the randomized population analyzed in the treatment group to which they were randomized. Analyses for the safety population will be included in the appendices if the size of the safety population is different (>10%) from the size of that in the primary analysis population for any treatment group.

Parameters described in [Section 2.1.1](#) will be summarized by treatment group and overall treatment groups using descriptive statistics.

Medical and surgical history will be summarized by treatment group and by system organ class (SOC) and preferred term (PT) sorted by internationally agreed order of SOC and by the decreasing frequency of PT within SOC based on the overall incidence across treatment groups. Atopic medical history will be summarized separately.

No statistical testing on demographic and baseline characteristic data will be performed.

No specific description of the safety parameters will be provided at baseline. If relevant, the baseline values will be described along with each safety analysis.

2.4.2 Prior or concomitant medications

The prior and concomitant medications will be presented for the randomized population.

Medications will be summarized by treatment group according to the WHO-DD dictionary, considering the first digit of the anatomic category (ATC) class (anatomic category) and the first 3 digits of the ATC class (therapeutic category). All ATC codes corresponding to a medication will be summarized, and patients will be counted once in each ATC category (anatomic or therapeutic) linked to the medication. Therefore patients may be counted several times for the same medication.

The table for prior medications will be sorted by decreasing frequency of ATC followed by all other therapeutic classes based on the overall incidence across treatment groups. In case of equal frequency regarding ATCs (anatomic or therapeutic categories), alphabetical order will be used.

Concomitant medication received during first IMP to last IMP +14 days and concomitant medication received during first IMP to last IMP +98 days will be summarized separately. The tables for concomitant medications will be sorted by decreasing frequency of ATC followed by all other therapeutic classes based on the incidence in the dupilumab 300 q2w group. In case of equal frequency regarding ATCs (anatomic or therapeutic categories), alphabetical order will be used.

In addition, inhaled corticosteroid in combination with other controllers and reliever medications will be summarized separately.

On a daily basis throughout the study, the patient uses an electronic diary to record daily use of ICS in combination with other controllers as used just prior to screening. The controller drugs will not be dispensed or supplied by the sponsor.

2.4.2.1 ICS in combination with other controllers

ICS and other asthma controller medications will be identified as the medications reported on the 'Prescribed Asthma Controller Medications' eCRF page.

Prior asthma controller medications will be summarized by treatment group sorted by decreasing frequency of standard medication name on the incidence in the overall treatment group.

Concomitant asthma controller medications will be summarized by treatment group sorted by decreasing frequency of standard medication name on the incidence in the dupilumab 300 q2w group.

The total daily dose of ICS in asthma controller medication at randomization will be classified as medium-dose or high-dose according to [Appendix C](#). If a patient takes more than one medication containing ICS, the ICS dose of different products will be standardized according to equivalent dose specified in [Table 4](#) and [Table 5](#). The equivalent dose is determined based on the thresholds in [Appendix C](#). After conversion, the total daily dose for inhaled corticosteroid will be calculated and classified as medium or high dose.

Table 4 – Equivalent dose for inhaled corticosteroids for adults and adolescents (≥ 12 years)

Inhaled corticosteroid	Equivalent dose (mcg) to 500 mcg Fluticasone propionate (DPI or HFA)
FLUTICASONE FUROATE	200-*
BECLOMETASONE DIPROPIONATE (CFC)	1000
BECLOMETASONE DIPROPIONATE (HFA)	400
BUDESONIDE (DPI)	800
CICLESONIDE (HFA)	320
MOMETASONE FUROATE	440
TRIAMCINOLONE ACETONIDE	2000

ADAPTED FROM GINA 2016 GUIDELINES

HFA=hydrofluoroalkane, DPI= Dry Powder Inhaler

* Fluticasone furoate (FF) dose ≥ 200 mcg is converted to equivalent fluticasone propionate (DPI or HFA) dose of $(FF \text{ dose} + 1) \times 2.5$; FF dose < 200 mcg is converted to equivalent fluticasone propionate (DPI or HFA) dose of $FF \text{ dose} \times 2.5$.

Example: A patient received 400 mcg budesonide (DPI) and 440 mcg mometasone furoate. They are equivalent to 250 mcg and 500 mcg fluticasone propionate correspondingly. The combined total daily dose is equivalent to 750 mcg fluticasone propionate and classified as high dose.

Table 5 – Equivalent dose of inhaled corticosteroid for adults and children (Japan)

Inhaled corticosteroid	Equivalent dose (mcg) to 400 Fluticasone propionate (DPI or HFA)
FLUTICASONE FUROATE	100
BECLOMETHASONE DIPROPIONATE -HFA	400
CICLESONIDE -HFA	400
BUDESONIDE-DPI	800
BUDESONIDE INHALATION SUSPENSION	1.0 mg
BUDESONIDE INHALATION SOLUTION	1000
MOMETASONE FUROATE-DPI	400

Adapted from Japanese Guideline for Adult Asthma 2014 and Japanese Guideline for Childhood Asthma 2014

Example: A patient received 400 mcg Beclomethasone dipropionate -HFA and 400 mcg Ciclesonide-HFA. They are both equivalent to 400 fluticasone propionate. The combined total daily dose is equivalent to 800 fluticasone propionate.

Number and percentage of patients on high-dose ICS, medium-dose ICS, any non-ICS controller medication, LABA, LAMA and LTRA at baseline will also be summarized.

2.4.2.1.1 Compliance

During the study, the daily intake of each prescribed asthma controller medication will be recorded on the electronic diary every evening. Compliance for the controller medications with ICS component and overall compliance to all prescribed controller medications will be calculated for each patient. For each day, a patient is considered as compliant with the prescribed controller medication with ICS component if the actual dose of each controller medication with ICS component is same as or greater than the prescribed dose. Similarly, a patient is considered as compliant with all controller medication if the actual dose of each controller medication is same as or greater than the prescribed dose.

Compliance for controller medication(s) with ICS component is defined as the number of days when the patient is compliant with the prescribed controller medication(s) with ICS component divided by the number of days the patient stays in the treatment period (from first dose to last dose + 14 days). **Overall controller medication(s) compliance** is defined as the number of days when the patient is compliant with all prescribed controller medication divided by the number of days the patient stays in the treatment period.

2.4.3 Extent of investigational medicinal product exposure and compliance

The extent of IMP exposure and compliance will be assessed and summarized by actual treatment within the safety population ([Section 2.3.2](#)).

2.4.3.1 Extent of investigational medicinal product exposure

The extent of IMP exposure will be assessed by the duration of IMP exposure.

Duration of IMP exposure is defined as last dose date – first dose date + 14 days, regardless of unplanned intermittent discontinuations (see [Section 2.5.3](#) for calculation in case of missing or incomplete data).

Duration of IMP exposure will be summarized descriptively as a quantitative variable (number, mean, SD, median, minimum, and maximum). In addition, duration of treatment exposure will also be summarized categorically by numbers and percentages for each of the following categories and cumulatively according to these categories:

- >0 and \leq 2 weeks
- >2 and \leq 4 weeks
- >4 and \leq 8 weeks
- >8 and \leq 12 weeks
- >12 and \leq 16 weeks
- ...
-

>48 and \leq 52 weeks

>52 weeks

Additionally, the cumulative duration of treatment exposure will be provided, defined as the sum of the duration of treatment exposure for all patients, and will be expressed in patient years.

2.4.3.2 Compliance

A given administration will be considered noncompliant if the patient did not take the planned dose of treatment as required by the protocol. No imputation will be made for patients with missing or incomplete data.

Percentage of compliance for a patient will be defined as the number of administrations that the patient was compliant divided by the total number of administrations that the patient was planned to take during the treatment epoch defined in [Section 2.1.4](#).

Above-planned dosing percentage for a patient will be defined as the number of administrations that the patient took a higher dose than planned divided by the total number of administrations that the patient was planned to take during the treatment epoch.

Under-planned dosing percentage for a patient will be defined as the number of administrations that the patient took a lower dose than planned divided by the total number of administrations that the patient was planned to take during the treatment epoch.

Treatment compliance, above-planned, and under-planned dosing percentages will be summarized descriptively as quantitative variables (number, mean, SD, median, minimum, and maximum). The percentage of patients whose compliance is <80% will be summarized. In addition, numbers and percentages of patients with at least 1 above-planned dose administration will also be provided, as well as numbers and percentages of patients with 0, (0, 20%], and >20% under-planned dose administrations.

Cases of overdose (defined as at least twice the intended dose during an interval of less than 11 days) will constitute serious adverse events and will be listed as such. More generally, dosing irregularities will be listed in [Section 2.2.1](#).

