- h* Prior to screening, patients must be on a stable background therapy of a medium to high dose of inhaled corticosteroid (ICS) in combination with a second controller medication (eg, long-acting beta agonist [LABA], leukotriene receptor antagonist [LTRA], methylxanthine, etc) for at least 3 months with a stable dose  $\geq 1$  month prior to Visit 1. Patients requiring a third controller are allowed to participate in this study. The third controller should also be used for at least 3 months with a stable dose  $\geq 1$  month prior to Visit 1 (patients requiring systemic steroids as controller medication or biologics are excluded).
- i* Every 2 week (q2w) investigational product administrations must be separated by at least 11 days. The randomized Treatment Period visits occur every 2 weeks up to Week 12 and then every 4 weeks, alternating with q2w home administration of IMP (patient, caregiver, or health care professional) without study visit up to the end of treatment period at Week 52. After Week 12, if the patient or Investigator decides not to administer IMP at home, the IMP injections can be performed at the site by way of unscheduled visits. Patients will be monitored at the study site for a minimum of 30 minutes after injections in the first 12 weeks.
- j* Electronic diary/PEF meter is used for daily recording of salbutamol/albuterol or levalbutamol/levolbuterol use, asthma controller drug use, oral steroid requirements, nocturnal awakenings due to asthma symptoms, morning and evening asthma symptom NRS scores and AM and PM PEF. This device is dispensed at Visit 1 and information is downloaded from this device on the other indicated days.
- k* ACQ-7 is completed in the patient's electronic diary during clinic visits. ACQ-7 (Asthma Control Questionnaire 7-question version) score will be used to follow up evaluations in all patients. ACQ-5 (the first 5 items of the ACQ-7) score is used for eligibility evaluation at visit 1 and visit 2 for all patients and follow up evaluations in all patients.
- l* Exhaled nitric oxide assessment is conducted prior to spirometry and following a fast of  $\geq 1$  hour.

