#### **8.1.4 Dosing schedule**

Two injections of IMP will be administered on Day 1 at Visit 2 as a loading dose. Subsequently one injection of IMP will be given every  $14 \pm 3$  days (q2w). The doses of investigational product must be separated by  $\geq 11$  days to avoid an overdose.

The Investigator or delegate will train the patient (or caregiver(s)) how to prepare and inject IMP at Visit 2 and will inject the first of the 2 injections. The patient (or caregiver(s)) will perform the second injection under the supervision of the Investigator or delegate. This training must be documented in the patient's study file. At subsequent study visits, patients are trained to self-inject IMP, and the patients are allowed to self-inject IMP at home after 6 injections at investigational site, counting from Visit 3.

Patients should be instructed to avoid missing any doses of medication during the study. Any patient who misses one dose should be reminded to be diligent, in order to avoid further missing doses thereafter. In case of missed dose(s) no loading dose of 2 injections will be administered when restarting the treatment, whatever the number of missed doses. The patients should continue on their scheduled IMP treatment and visit, even if more than 2 consecutive doses are missed.

When the patient has a study visit, the IMP will be administered following clinic procedures and blood collection. Patients should be monitored for at least 30 minutes after each study-site administered investigational product administration for any signs or symptoms of a hypersensitivity reaction.

For doses not given at the study site, diaries will be provided to record information related to the injections. The diary will be kept as source data in the patient's study file.

If the patient (or caregiver) is unable or unwilling to administer IMP, arrangements must be made for qualified site personnel and/or health care professionals (eg, visiting nurse service) to administer IMP for the doses that are not scheduled to be given at the study site.

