#### **10.4.1.3 Adverse event of special interest**

An adverse event of special interest (AESI) is an AE (serious or non-serious) of scientific and medical concern specific to the Sponsor's product or program, for which ongoing monitoring and immediate notification by the Investigator to the Sponsor is required. Such events may require further investigation in order to characterize and understand them. Adverse events of special interest may be added or removed during a study by protocol amendment.

For these AESIs, the Sponsor will be informed immediately (ie, within 24 hours), per SAE notification described Section 10.4.4, even if not fulfilling a seriousness criterion, using the corresponding pages in the CRF (to be sent) or screens in the e-CRF.

- Anaphylactic reactions or systemic allergic reactions that are related to IMP and require treatment (refer to Appendix M for Definition of Anaphylaxis)
- Severe injection site reactions that last longer than 24 hours
- Any infection meeting at least one of the following criteria:
  - Any serious infection (SAE)
  - Requires parenteral (intravenous, intramuscular, subcutaneous) antimicrobial therapy
  - Requires oral antimicrobial therapy for longer than 2 weeks
  - Is a parasitic infection
  - Is an opportunistic infection (see [Appendix N](#))

Note: antimicrobial therapy refers to antibiotic, antiviral, and antifungal agents

- Significant ALT elevation
  - ALT >5 x the upper limit of normal (ULN) in patients with baseline ALT  $\leq$ 2 x ULN;  
or
  - ALT >8 x ULN if baseline ALT >2 x ULN
- Pregnancy of a female subject entered in a study as well as pregnancy occurring in a female partner of a male subject entered in a study with IMP/Noninvestigational medicinal product (NIMP);
  - Pregnancy occurring in a female patient entered in the clinical trial or in a female partner of a male patient entered in the clinical trial. It will be qualified as an SAE only if it fulfills one of the seriousness criteria (see Section 10.4.1.2).
  - In the event of pregnancy in a female participant, IMP should be discontinued.
  - Follow-up of the pregnancy in a female participant or in a female partner of a male participant is mandatory until the outcome has been determined.
- Symptomatic overdose (serious or non-serious) with IMP/NIMP

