  - An overdose (accidental or intentional) with the IMP is an event suspected by the Investigator or spontaneously notified by the patient and defined as at least twice the intended dose during an interval of less than 11 days. The circumstances (ie, accidental or intentional) should be clearly specified in the verbatim and symptoms, if any, entered on separate adverse event forms.
  - An overdose (accidental or intentional) with any NIMP is an event suspected by the Investigator or spontaneously notified by the patient and defined as at least twice of the intended dose within the intended therapeutic interval. The circumstances (ie, accidental or intentional) should be clearly specified in the verbatim and symptoms, if any, entered on separate AE forms.

Of note, asymptomatic overdose has to be reported as a standard AE.

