- All treatment-emergent adverse events by primary SOC and PT, showing the number (%) of patients with at least 1 treatment-emergent adverse event, sorted by the internationally agreed SOC order and by decreasing incidence of PTs within each SOC.
- All treatment-emergent adverse events regardless of relationship and related by primary SOC, HLG, HLT and PT, showing the number (%) of patients with at least 1 treatment-emergent adverse event, sorted by the internationally agreed SOC order. The other levels (HLG, HLT, PT) will be presented in alphabetical order
- All treatment-emergent adverse events by maximal severity, presented by primary SOC and PT, showing the number (%) of patients with at least 1 treatment-emergent adverse event by severity (ie, mild, moderate, or severe), sorted by the internationally agreed SOC order and by decreasing incidence of PTs within each SOC
- Number (%) of patients experiencing treatment-emergent adverse event(s) presented by primary and secondary SOC, HLG, HLT, and PT sorted by the internationally agreed SOC order. The other levels (HLG, HLT, PT) will be presented in alphabetical order

- A listing of all treatment-emergent adverse events will be presented

Analysis of all treatment-emergent serious adverse event(s)

- All treatment-emergent serious adverse events by primary SOC, HLG, HLT, and PT, showing the number (%) of patients with at least 1 serious treatment-emergent adverse event, sorted by the internationally agreed SOC order. The other levels (HLG, HLT, PT) will be presented in alphabetical order
- All treatment-emergent serious adverse events regardless of relationship and related to IMP, by primary SOC, HLG, HLT, and PT, showing the number (%) of patients with at least 1 treatment-emergent serious adverse event, sorted by the internationally agreed SOC order. The other levels (HLG, HLT, PT) will be presented in alphabetical order
- All treatment-emergent serious adverse events by primary SOC and PT, showing the number (%) of patients with at least 1 treatment-emergent serious adverse event, sorted by the internationally agreed SOC order and by decreasing incidence of PTs within each SOC.
- A listing of all treatment-emergent serious adverse events will be presented

Analysis of all treatment-emergent adverse event(s) leading to permanent treatment discontinuation or drug interruption

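### SAP 2.4.3.2 makes every overdose of study drug a serious adverse event, whereas protocol 10.4.1.3, on the same dose and interval threshold, allows overdoses to be non-serious

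*SAP*

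**What the plan says.** SAP 2.4.3.2 closes its account of treatment compliance with this rule: "Cases of overdose (defined as at least twice the intended dose during an interval of less than 11 days) will constitute serious adverse events". In full, such cases "will constitute serious adverse events and will be listed as such". No exception is made for symptoms or for seriousness criteria. The sentence does not name the investigational product, but its parent section does: "The extent of IMP exposure and compliance will be assessed and summarized by actual treatment within the safety population".

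Protocol 10.4.1.3 defines an overdose of the investigational product by the same dose multiple and the same interval. It then separates two cases. The first is an adverse event of special interest (AESI): "Symptomatic overdose (serious or non-serious) with IMP/NIMP". The second is not: "Of note, asymptomatic overdose has to be reported as a standard AE". The same section states that AESIs are notified by the route used for serious adverse events (SAEs) even when they meet no seriousness criterion, so notification by that route does not make an event serious.

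Protocol 10.4.1.2 defines an SAE by criteria. Overdose is not among its examples of medically important events, though that list is expressly open-ended.

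**The concern.** The SAP fixes the seriousness of a whole class of events by a rule in its compliance section. The protocol leaves seriousness to the criteria in 10.4.1.2 and says explicitly that an overdose may fail to meet them. Someone programming from SAP 2.4.3.2 would produce a listing of serious overdoses containing events that investigators had correctly recorded as non-serious.

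SAP 2.4.5.1 separately promises: "A listing of all treatment-emergent serious adverse events will be presented". If that output uses reported seriousness, the two listings contradict each other for the same event. If the data were recoded to agree with 2.4.3.2, counts of serious events would include events that meet no seriousness criterion. The SAP does not say which would happen.

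**Working it through.** The plan gives no figure to reproduce, so the check is a comparison of the passages, case by case.

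| Overdose of study drug | Protocol 10.4.1.2 and 10.4.1.3 | SAP 2.4.3.2 | Agree? |
|---|---|---|---|
| Symptomatic, meets a seriousness criterion | AESI, serious | SAE | Yes |
| Symptomatic, meets no seriousness criterion | AESI, non-serious | SAE | No |
| Asymptomatic | Standard AE | SAE | No |

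**Is the definition the same?** The dose multiple and the interval are identical. The protocol adds that the event is one the investigator suspects or the patient reports unprompted, and the SAP omits this. The omission does not resolve the conflict: an event that satisfies the protocol's fuller definition also satisfies the SAP's.

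**Is the rest of the SAP consistent with the sentence?** It is not.
- Table 3 in SAP 2.1.4.1 identifies symptomatic overdose from a yes answer on the adverse event form and requires no serious status. Other rows of that table, such as severe or serious infection, do name serious status where it matters.
- For each AESI grouping, SAP 2.4.5.1 counts patients with any treatment-emergent event and patients with a treatment-emergent serious event separately. If every overdose were serious, those two counts would be equal by construction for the overdose grouping.

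**Was a change declared?** SAP 1.5 and 1.6 do not mention reclassifying overdoses. Those tables cover major changes only, so this is weak evidence. It does mean that nothing shows the rule to be deliberate.

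**How easily is the definition met?** Protocol 8.1.4 sets dosing every 14 ± 3 days:
- earliest planned interval: 14 − 3 = 11 days;
- latest planned interval: 14 + 3 = 17 days.

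Two single doses 10 days apart amount to 2 × the intended dose in an interval of 10 < 11 days, so the definition is met. At exactly 11 days it is not met, because 11 is not less than 11. A single syringe given one day before the window opens is therefore enough on this reading. Section 8.1.4 supports the reading, since it gives the reason for the spacing as "days to avoid an overdose". Footnote i of the flow chart in protocol 1.2 repeats only the spacing rule ("investigational product administrations must be separated by at least 11 days") and does not mention overdose.

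The overdose row of the reporting-timeline table in protocol 10.4.3 is broken in the available text and was not used.

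**The case against.** The strongest reply is that the sentence has no working effect. It sits at the end of a compliance section, promises only a listing, and gives no derivation or recoding rule. The serious-event outputs are specified elsewhere, in SAP 2.4.5.1, without reference to it. For a different variable, missing causal relationship, SAP 2.5.3 forbids imputation at the data level, and nothing in the SAP suggests that reported seriousness would be overridden. In practice the seriousness flag on the case report form would probably be used.

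This limits the weight of the point. No effect on tables of serious events has been shown. It does not remove the point: if the reported flag is what will be used, the sentence in 2.4.3.2 is wrong and should go.

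Three smaller objections:
- The 10-day example is an inference, since neither definition says that one early syringe is an overdose, and the protocol also requires the event to be suspected or reported. This is fair. The example shows how low the threshold is, and the contradiction does not depend on it.
- In the protocol, a standard adverse event is contrasted with an AESI, which is partly a matter of reporting route. An asymptomatic overdose could in principle still be judged medically important. That would be a case-by-case judgment, whereas the SAP makes every such event serious.
- The protocol's compliance section 11.4.1.2 has no such rule either, but it does not discuss overdose at all, so its silence shows little.

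**Conclusion.** The contradiction is real and no other passage resolves it. Of the three kinds of overdose the protocol distinguishes, the SAP sentence agrees with one and misclassifies two. Confidence is high on the textual mismatch and lower on any downstream effect, because the SAP does not say whether seriousness would be recoded.

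The size is minor. What follows directly from the text is a listing that labels non-serious events as serious. A disagreement between listings assumes that the SAP 2.4.5.1 listing uses reported seriousness, and an effect on counts of serious events assumes recoding. The number of affected patients cannot be derived, since the documents give no frequency of overdose. No efficacy analysis, type I error or power is involved.

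**What to change.** Reconcile SAP 2.4.3.2 with protocol 10.4.1.2 and 10.4.1.3 and with SAP Table 3. Keep the dose and interval definition in 2.4.3.2 and replace the rest of the sentence with wording such as:

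> Overdoses meeting this definition will be listed, showing seriousness as the investigator reported it under protocol 10.4.1.2 and AESI status under protocol 10.4.1.3.

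If the sponsor did intend all overdoses to count as serious, the protocol and SAP must be brought into agreement and the change recorded in SAP 1.6.

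The recommended change costs one SAP sentence. It needs no new data, no new analysis and no change to dosing or patient management.
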